6.1 Recombinant Human DNase (dornase alfa)

Genentech (a wholly owned subsidiary of Roche) and Chugai Pharmaceutical developed and launched an inhalation solution (Pulmozyme) of dornase alfa, a highly purified recombinant human deoxyribonuclease (dornase alfa), for daily administration in conjunction with standard therapies. The product is indicated for the management of people with cystic fibrosis (CF) to improve pulmonary function. Dornase alfa is safe and well tolerated in adults and children.

Dornase alfa was launched in the US for the management of mild-to-moderate CF in conjunction with standard therapies in January 1994; in December 1996, the FDA expanded approval for use in CF participants with advanced CF. In April 1994, the drug was launched in the UK and Ireland, and by October 1994, it had been launched in France and Germany. In June 2012, dornase alfa was launched in Japan for the improvement of pulmonary function in participants with CF.

In December 2014, the FDA approved the eRapid Nebuliser System from PARI to deliver dornase alfa and to reduce treatment times (three minutes to deliver 2.5mg).

The recommended dosage is one 2.5 mg single-use ampule inhaled once daily using a recommended nebuliser jet nebuliser/compressor system or eRapid[™] Nebuliser System. Some participants (older/refractory) benefit from twice daily administration. (FDA label and EMA SmPC).

The most common adverse reactions (occurring in \ge 3% of participants treated with dornase alfa over placebo) seen in clinical trials in CF participants were: voice alteration, pharyngitis, rash, laryngitis, chest pain, conjunctivitis, rhinitis, decrease in FVC of \ge 10%, fever, and dyspnoea.

6.2 Source of dornase alfa, manufacture and distribution

Dornase alfa inhalation solution is a sterile, clear, colourless solution supplied in 30 unit cartons containing 5 foil pouches of 6 single-use ampules. Each 2.5 mL ampule contains 2.5mg of dornase alfa (1 mg/mL): NDC 50242-100-40.

Dornase alfa will be prescribed by the CI (or designee) and dispensed to patients via hospital stock. Alternatively, dornase alfa will be supplied directly from the manufacturer (Roche) as required. Handling and management of dornase alfa will be subject to standard procedures of the pharmacy. The dornase alfa will not be modified in any way, but administered as approved.

6.3 Storage and handling of dornase alfa

Dornase alfa is stored under refrigeration (2°C to 8°C/36°F to 46°F) in their protective foil to protect from light. Dornase alfa should not be used beyond the expiration date stamped on the ampule. Unused ampules must be stored in their protective foil pouch under refrigeration. Dornase alfa must be refrigerated during transport and not exposed to room temperatures for a total time of 24 hours.

6.4 Accountability of dornase alfa

The Drug Accountability Log must be completed to record each dose of dornase alfa dispensed for each trial participant. This log must be retained in the relevant section of the Pharmacy Site File, and a copy must be submitted to the sponsor upon request. It is the responsibility of the Pharmacy Lead to maintain drug accountability records.

All used/unused ampules maybe returned to site pharmacy, to be then updated in the drug accountability log in the pharmacy site file. Following authorisation by the sponsor, drug destruction will be conducted in accordance to local practice, and this will be documented in the drug destruction log in the hospital pharmacy file.

Detailed instructions are contained in the summary of drug arrangements.

6.5 Concomitant medication

Participants in the COVASE trial will continue to receive best available care (BAC) per UCLH guidelines. Dornase alfa will be administered in addition to BAC.

BAC currently consists of symptomatic relief: antipyretics, analgesics and intravenous fluids if needed. In addition, patients may need supplemental oxygen and/or mechanical ventilation.

There is no basis to support a drug-drug interaction risk, as this is a recombinant human protein that is administered directly to the lungs. Systemic exposure is very low and dornase alfa is cleared by proteinases present in the lungs.

There is a potential risk that other medications administered as BAC may affect the endpoints in the study e.g. decrease CRP. However, this cannot be avoided and will be considered in the analysis plan for the data. Furthermore, a sample-size re-estimation is planned in order to take this potential source of unexpected variability into account.

Concomitant medications will be recorded in the participant's medical records/CRF.

6.6 Post-trial IMP arrangements

No specific arrangements required.

7 Selection of participants

People who are at high probability of COVID-19 and admitted to hospital will be identified from inpatient lists and approached, pending COVID PCR results (12 hours). They will be given a patient information sheet (PIS) with details of the clinical trial to read before deciding on entry into the COVASE trial.

7.1 Eligibility of trial participants

7.1.1 Trial participant inclusion criteria

1. Male and female participants, aged \geq 18 years

- 2. Participants who are hospitalised for suspected Coronavirus (SARS-CoV)-2 infection confirmed by polymerase chain reaction (PCR) test or radiological confirmation with chest CT
- 3. Participants with stable oxygen saturation (>=94%) on supplementary oxygen
- 4. CRP >= 30 mg/L
- 5. Participants will have given their written informed consent to participate in the study and are able to comply with instructions and nebuliser

7.1.3 Trial participant exclusion criteria

- 1. Females who are pregnant, planning pregnancy or breastfeeding
- 2. Concurrent and/or recent involvement in other research or use of another experimental investigational medicinal product that is likely to interfere with the study medication within (specify time period e.g. last 3 months) of study enrolment
- 3. Serious condition meeting one of the following:
 - i. Respiratory distress with respiratory rate >=40 breaths/min
 - ii. oxygen saturation<=93% on high-flow oxygen
- 4. Require mechanical invasive or non-invasive ventilation at screening
- 5. Concurrent severe respiratory disease such as asthma, COPD and/or ILD
- 6. Any major disorder that in the opinion of the Investigator would interfere with the evaluation of the results or constitute a health risk for the trial participant
- 7. Terminal disease and life expectancy <12 months without COVID-19
- 8. Known allergies to dornase alfa and excipients
- 9. Participants who are unable to inhale or exhale orally throughout the entire nebulisation period

7.2 Recruitment

Participants will be recruited from inpatients at UCLH.

Participant recruitment will only commence when the trial has been issued with the 'Open to Recruitment' letter by the Sponsor.

Recruitment rate is estimated to range from 3 to 6 participants per week. Recruitment is estimated to take 12-15 weeks.

7.3 Informed consent procedure

It is the responsibility of the Investigator, or a person delegated by the Investigator to obtain written informed consent from each participant prior to participation in the trial, following adequate explanation of the aims, methods, anticipated benefits and potential hazards of the trial.

The person taking consent will be GCP trained, suitably qualified and experienced, and will have been delegated this duty by the CI/ PI on the Staff Signature and Delegation of Tasks.

"Adequate time" must be given for consideration by the participant before taking part. Due to the rapidly escalating situation, consent will be sought after giving the participant adequate time

to consider their decision after being given the study documentation. Patients will be given additional time up to 18 hours if needed. It must be recorded in the medical notes when the participant information sheet (PIS) has been given to the participant.

The Investigator or designee will explain that participants are under no obligation to enter the trial and that they can withdraw at any time during the trial, without having to give a reason.

No clinical trial procedures will be conducted prior to the participant giving consent by signing the Consent form. Consent will not denote enrolment into trial.

A copy of the signed informed consent form will be given to the participant. The original signed form will be retained in the trial file at site and a copy placed in the medical notes.

The PIS and consent form will be reviewed and updated if necessary, throughout the trial (e.g. where new safety information becomes available) and participants will be re-consented as appropriate.

8 Trial procedures

8.1 **Pre-treatment Assessments**

The following trial specific procedures will be carried out after consent and within 3 days of treatment to assess the participant's eligibility:

- Informed consent
- Medical history
- Physical examination
- Vital signs
- Pregnancy test (urine)
- Whole blood count and differential
- Oxygen saturation and record oxygen delivery device if applicable (can be repeated if necessary)
- Oxygen requirement
- Blood draw for PD
- Blood draw for biomarkers
- Clinical Laboratory assessments including CRP, d-dimer and PCT (can be repeated if necessary)
- Concomitant medications

All pre-treatment procedures will be carried out as specified in the schedule of assessments (Appendix 1).

8.2 Randomisation Procedures

Participant randomisation will be undertaken centrally by an independent statistician (ie not the trial statistician) using SAS PROC PLAN according to SOPs. The randomisation schedule will be maintained in a secure, password protected environment, inaccessible to others supporting the trial.

Following participant consent, and confirmation of eligibility (see section 8.1 for pre-treatment assessments) the randomisation procedure described below will be carried out.

Participants are considered to be enrolled into the trial following: consent, pre-treatment assessments (see section 8.1), confirmation of eligibility, completion of the randomisation process, allocation of the participant trial number and treatment by the central coordinating team.

8.3 Treatment Schedule

Dornase alfa will be nebulised at 2.5mg twice per day (12 \pm 3 hours apart) for seven days using either:

- the recommended eRapid Nebuliser System, consisting of the eRapid[™] Nebuliser Handset with eBase[™] Controller OR
- a jet nebuliser connected to an air compressor with an adequate air flow and equipped with a mouthpiece (Table 1).

Jet nebuliser	Compressor
Hudson T Up-draft II with	Pulmo-Aide
Marquest Acorn II with	Pulmo-Aide
PARI LC Plus with	PARI PRONEB
Durable Sidestream with	MOBILAIRE™
Durable Sidestream with	Porta-Neb

Table1 Recommended Jet Nebulisers/Compressors

8.3.1 Dose modifications

Based on clinical judgement, it may be decided to extend the dosing period for some participants. For example, a change from 2.5mg BID for 7 days to 2.5mg BID for up to 14 days. In particular, if participants have significant benefits from therapy, but show relapses of the COVID-19 inflammatory state (rising CRP and increasing oxygen requirements in the absence of bacterial infection), on completing 7 days of treatment, then the medical team have the choice of reinstating dornase alfa treatment for up to 7 further days (14 days in total) at 2.5mg BID. Blood sampling will continue until the last day of dosing with dornase alfa.

8.4 Subsequent assessments and procedures

8.4.1 Schedule of assessments

The following assessments and procedures will take place on Day1, Day3, Day5 and Day7 of dosing. In participants who remain on treatment beyond Day7, assessments will occur on Day9, Day11 and Day14 of dosing.

- Eligibility confirmation (at Day1 only)
- o Physical examination

- Vital signs (Blood pressure, heart rate, temperature, respiration rate)
- o Whole blood count and differential
- Oxygen saturation and record oxygen delivery device if applicable
- Oxygen requirement (oxygen flow or oxygenation index)
- \circ $\;$ Blood draw and bronchial secretions (when available) for PD $\;$
- o Blood draw and bronchial secretions (when available) for biomarkers
- Clinical Laboratory assessments including CRP, d-dimer and PCT (can be repeated if necessary)
- Multi-organ failure according to SOFA (Sepsis-related Organ Failure Assessment)
- Acute physiology score + age points + chronic health points (APACHE score) data that has been collected to calculate this score.
- Ordinal score (WHO scoring tool)
- Adverse Events review
- o Concomitant Medication review

Other assessments to be recorded if/when they occur:

- Length of ICU stay (hours)
- Length of stay in the hospital (days)
- Length of time on mechanical ventilation (days)
- Ventilator-associated pneumonia (VAP) or hospital-acquired pneumonia
- Survival (days)

Assessments/procedures at follow-up. These assessments and procedures will occur before the participant is discharged from the hospital or Day35, whichever comes first.

- Physical examination
- Vital signs (Blood pressure, heart rate, temperature, respiration rate)
- Pregnancy test (urine)
- Whole blood count and differential
- Oxygen saturation and record oxygen delivery device if applicable
- Oxygen requirement (oxygen flow or oxygenation index)
- Blood draw for PD
- Blood draw for biomarkers
- Clinical Laboratory assessments including CRP, d-dimer and PCT (can be repeated if necessary)
- Multi-organ failure according to SOFA (Sepsis-related Organ Failure Assessment)
- Acute physiology score + age points + chronic health points (APACHE score) data that has been collected to calculate this score.
- Ordinal score (WHO scoring tool)
- Adverse Events review (daily)
- o Concomitant Medication review

Other assessments to be recorded if/when they occur:

- Length of ICU stay (hours)
- Length of stay in the hospital (days)
- Length of time on mechanical ventilation (days)
- Ventilator-associated pneumonia (VAP) or hospital-acquired pneumonia

• Survival (days)

In participants who are discharged before Day35, a telephone call will occur at Day35 to ask them about their breathing e.g. Are you short of breath? Has your breathing returned to the same level as previously?

A schedule of all trial assessments and procedures is set out in Appendix 1.

8.5 Laboratory Assessments and Procedures

Local laboratories will be used for the primary and secondary assessments and procedures. These include CRP, whole blood count and differential count, proCalcitonin (PCT), and D-Dimer. The samples will be taken as per hospital standard procedures as part of routine clinical care.

Laboratory test	Parameters
BLOOD	
Haematology	leukocytes, erythrocytes, haemoglobin, haematocrit, mean corpuscular volume (MCV), mean corpuscular haemoglobin (MCH), platelets, neutrophils, eosinophils, basophils, lymphocytes, monocytes
Serum chemistry	glutamate pyruvate transaminase (GPT / ALAT), glutamic- oxaloacetic transaminase (GOT / ASAT), gamma-glutamyl transferase (gamma-GT), alkaline phosphatase, total bilirubin, creatinine, chloride, potassium, sodium, total protein, albumin, Lactate, Renal function: (Creatinine, Urea and Na, K, Cl), Clotting screen including Prothrombin time, Bone profile (ca2+), High- sensitivity troponin, Ferritin, LDH, Creatinine
Biomarkers	CRP, PCT, D-dimer

The following tests will be carried out at Local Laboratories:

PD and biomarkers (exploratory) samples

The volume of blood required for PD and biomarkers exploratory endpoints is 10ml.

When it is available, bronchial secretions may be collected to measure PD and biomarkers. The bronchial secretion will be obtained due to spontaneous expectoration or route clinical bronchoscopy during MV.

All samples for exploratory endpoints (biomarkers and PD) will be labelled with the unique identifying number (UIN) prior to transfer to The Francis Crick Institute. Samples will be stored in secure UCL research facilities with restricted access under the custodianship of the Chief Investigator or designee until the samples are shipped by courier.

Transfer of samples for exploratory endpoints (biomarkers and PD) to The Francis Crick Institute will be subject to a laboratory agreement in which the Francis Crick Institute will be responsible for restricting use of the samples and data to agreed purposes, maintenance of confidentiality and data security, reporting publications and other outputs to the chief investigator of this trial and restricting onward transfer of samples to a third party. PD and biomarker samples will be collected under the supervision of the Chief Investigator (or designee) and send to The Francis Crick Institute with courier to a dedicated person in the laboratory of [name]. Blood (up to 10 mL – vacutainers- heparin or EDTA) and bronchial secretions will be transferred to The Francis Crick institute. Samples will be processed and stored for further analysis in the Francis Crick Institute Freezer Farm. Tracking of samples will be done with Freezerpro data base. Research samples will be processed in the Crick laboratories by designated research staff within an SOP (COVASE SOP) under the supervision of [name].

Exploratory samples (blood draw and bronchial secretion for PD and biomarkers – Appendix I)

Sample processing:

1) Leukocyte pelleting for RNA extraction and sequencing (biomarker).

2) Plasma collected for: Haemolysis (biomarker); cytokine analysis by ELISA and multiplex panel for 67 markers of inflammation (biomarker); coagulation markers such fibrin, tissue factor, Von Willebrand factor, thrombin, thromboxane A2 (biomarker), complement cascade markers such as C1q, (biomarker), quantification of NETs by NET ELISA (PD), quantification of cell-free DNA (PD) and in vitro NET formation assays (biomarker).

 Plasma samples denatured and boiled in SDS for Western immunoblotting to assess neutrophil markers such as neutrophil elastase; myeloperoxidase; histones; citrullinated H3. (PD).

4) Bronchial secretions will be processed according to local procedures for the measurement of biomarkers.

These samples will be handled at containment level 2 according to local guidelines.

treatment arm	blood at each timepoint	number of blood draw timepoints	Number of days in the trial	total blood over the trial
BAC for 7 days	30mL	6	35 days	180mL
Dornase alfa for 7 days	30mL	6	35 days	180mL
Dornase alfa for 14 days	30mL	9	35 days	up to 270mL

Total blood draw/participant

8.6 Clinical Procedures and Data Collection

All study procedures will be carried out by UCLH medical staff in the hospital and as specified in UCLH guidelines.

Medical examination: The following sites will be examined: head, neck, ears, nose, throat, eyes, chest, lungs, heart, abdomen, skin, and lymph nodes; and the following systems will be assessed: musculoskeletal and neurological.

8.7 Assessment of dornase alfa compliance

Monitoring (e.g. watching participant inhale dornase alfa) and recording this appropriately.

8.8 Discontinuation/withdrawal of participants

In consenting to participate in the trial, participants are consenting to trial treatment, assessments, follow-up and data collection.

Discontinuation of trial treatment for clinical reasons

A participant may be withdrawn from trial treatment whenever continued participation is no longer in the participant's best interests, but the reasons for doing so must be recorded. Reasons for discontinuing treatment may include:

- Alternative clinical diagnosis emerges (no longer considered to have primary COVID-19 lung disease).
- Disease progression whilst on therapy.
- Unacceptable toxicity.
- Intercurrent illness which prevents further treatment.
- Patients withdrawing consent to further trial treatment.
- Any alterations in the participant's condition which justifies the discontinuation of treatment in the Cl's or designee's opinion.
- Persistent non-compliance to protocol requirements.
- Participant is put on end of life pathway and dies prior to dosing.

The decision to withdraw a participant from treatment must be recorded in the CRF and medical notes, and the sponsor when required should be notified in writing.

Participant withdrawal from trial treatment or follow-up

If a participant expresses their wish to withdraw from trial treatment or follow-up, sites should explain the importance of remaining on trial follow-up and seek permission to allow use of routine follow-up data to be used for trial purposes. The importance of safety follow-up should be emphasised to the participant in the Participant Information Sheet.

The decision of the participant to withdraw from treatment or follow-up must be recorded in the CRF and medical notes.

The participant may withhold their reason for withdrawal however, if the participant gives a reason for their withdrawal, this should be recorded.

Withdrawal of consent to data collection

If a participant explicitly states that they do not wish to contribute further data to the trial their decision will be respected and recorded in the CRF and medical notes.

8.9 Replacements

40 evaluable participants are required to meet the primary endpoint, Therefore, if a participant withdraws or is withdrawn, a replacement participant may be enrolled to the same treatment arm.

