Due to the evolving situation with hospitalised COVID-19 participants, the burden on the NHS and the availability of other COVID-19 trials, it is considered inappropriate to conduct a placebocontrolled study. Therefore, a randomised, controlled, open-label approach where dornase alfa is administered on top of BAC and compared to BAC alone has been adopted.

The data derived from the 10 participants who are randomised to the BAC arm of the study who do not receive dornase alfa will provide control data for all of the study endpoints.

The 30 participants randomized to BAC + dornase alfa will be compared to 10 randomised controls from the COVASE study. In addition, 10 participants in other clinical trials on BAC (biobanked samples) and 60 participants from a historic database of the first 120 people with COVID-19 treated at UCLH will also be used as comparator data.

However, to enhance the control group, a hybrid approach will be applied such that additional data will be combined with the randomised controls, illustrated in Figure 3. The sample size calculation indicates that 90 evaluable participants are required (60 control:30 active). These control data may include: data from the randomised BAC arm, historic COVID-19 UCLH database, biobanked samples from other ongoing trials and observational trials in COVID-19.

This hybrid strategy allows two things:

- provides comparators for all of the study objectives (including limited data for the exploratory objectives)
- demonstrates that the historic controls are representative/similar to the study population

Comparator data from UCLH is available as historic controls for the Primary and Secondary Endpoints. A database of the first 120 participants with COVID-19 admitted to UCLH is available and being analysed currently. CRP is routinely measured daily (or on alternate days) in all participants admitted to UCLH and will be used to control for the Primary Endpoint. All of the Secondary Endpoints are also routinely measured and will be available in the database. Participants in the database will be selected to act as controls as follows:

- 1. Apply the inclusion and exclusion criteria of the COVASE study
- 2. Additional selection to identify closest matches using a propensity score based on age, gender, BMI, baseline CRP, oxygen requirements and the number of comorbidities.

At least 60 control participants are expected to be available to act as controls.

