11.2 Sample size and recruitment

11.2.1 Sample size calculation

Sample size calculations were produced using the proc power function in SAS Version 9.4. These were conducted to achieve 80% power to detect difference in the active arm versus the control group at the 5% level of significance. Based on a mean of 99mg/L in the control group and a common standard deviation of 62mg/L derived from the literature (Han et al., 2020; Zhou, 2020), a total sample size of 90 participants would provide sufficient power to detect a greater than a 40% relative difference for CRP in the dornase alfa group compared to the control group. Given the reported average values in severe and non-severe participants and on clinical observations from COVID-19 patients, this difference would be achievable and clinically relevant.

This study will use existing data collected at UCLH from participants admitted with COVID-19 as a comparator group. Participants in the database will be selected to act as controls as follows:

- Apply the inclusion and exclusion criteria of the COVASE study
- Additional selection to identify closest matches

This will give the correct ratio of active versus comparator (ratio of 1:2). To achieve the required power, this would result in 30 participants in the active treatment group and at least 60 in the control. An additional 10 participants will be recruited as a control for the exploratory objectives and to compare the characteristics of enrolled participants with the historical controls. This gives a total of 40 participants enrolled in the study and 60 historical controls.

Participants who drop out of the study will be replaced so the sample size relates to the number of evaluable participants required.

A re-estimation of the sample size will be carried following an interim analysis when 12 participants have been randomised.

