11.2.2 Planned recruitment rate

The anticipated recruitment rate is 3-5 participants per week at UCLH. To obtain 40 participants, the recruitment period is likely to last between 8 and 14 weeks. Given the paucity of treatment options and the observed number of cases, the sample size should be easily attainable.

Randomisation methods

Subjects will be allocated to dornase alfa or BAC in a 3:1 ratio in accordance with the randomisation schedule. The randomisation schedule will be based on permuted block randomisation produced using SAS PROC PLAN. Block sizes will vary in multiples of 4.

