### 6. ANALYSIS POPULATIONS

The primary analysis will be conducted using the primary analysis population and is based on the ITT principle. Details on subjects enrolled but not included in the analysis populations will be presented as part of the CONSORT diagram.

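### Same-arm replacement (Protocol 8.9) bypasses the randomisation schedule, and an undefined evaluable count leaves open whether a replaced participant stays in the primary analysis

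*Protocol*

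**What the plan says.** **Replacement.** Protocol 8.9 opens with "40 evaluable participants are required to meet the primary endpoint" and goes on: "if a participant withdraws or is withdrawn, a replacement participant may be enrolled to the same treatment arm". Protocol 11.2.1 is firmer: "Participants who drop out of the study will be replaced so the sample size relates to the number of evaluable participants required". SAP section 5 repeats that sentence without mentioning the arm.

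**Allocation.** Under Protocol 11.2.2 assignment is 3:1: "The randomisation schedule will be based on permuted block randomisation produced using SAS PROC PLAN. Block sizes will vary in multiples of 4". Protocol 8.2 adds: "The randomisation schedule will be maintained in a secure, password protected environment, inaccessible to others supporting the trial". Neither section gives a reserve list or any other concealed route for replacements.

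**Blinding.** There is none. Protocol 5.1 says that "a randomised, controlled, open-label approach where dornase alfa is administered on top of BAC and compared to BAC alone has been adopted".

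**Who is analysed.** Protocol 11.3.1 builds the primary population from evaluable dornase alfa patients plus matched historical controls. SAP 6.1, headed as intention to treat, takes evaluable patients from both randomised arms who have at least one CRP after baseline, plus matched historical controls. Both documents say that the primary analysis "is based on the ITT principle". Neither defines *evaluable*, and neither says whether a replaced participant is still analysed.

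**Reasons for leaving treatment.** The list in Protocol 8.8 includes "Disease progression whilst on therapy".

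**The concern.** There are two separate problems.

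First, a participant enrolled to a named arm has not been randomised. Keeping the schedule secret does not protect that slot, because the schedule is not used for it. The leaver's arm is known on site, so the allocation can be predicted and could influence who is approached next. What is at stake is the comparison of dornase alfa with randomised BAC, which is the only fully randomised contrast in the plan. The BAC patients who enter the SAP primary analysis alongside the historical controls are affected too.

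Second, the word that triggers replacement (*evaluable*) is also the word that admits patients to the primary analysis. If a replaced participant were treated as not evaluable, someone who left for a reason related to outcome could be exchanged for a new patient while the analysis still carried the ITT label.

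**Working it through.** **1. The plan's own figure.** Inputs from Protocol 11.2.1 and SAP section 5: control mean 99 mg/L, SD 62 mg/L, 40% relative difference, 80% power, 5% level (two-sided, as SAP 11.1 implies), 1:2 allocation.

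- Difference = 0.40 × 99 = 39.6 mg/L.
- The normal approximation gives 29 + 58 = 87.
- A two-sample t-test has power 0.793 at 29:58 and 0.807 at 30:60.

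The stated 30 + 60 = 90 therefore reproduces, and the sample-size arithmetic is not in question. It does show that primary power rests on 30 active and 60 historical patients. The 10 BAC patients are recruited for the exploratory objectives and to check comparability, so the 40 that Protocol 8.9 ties to the primary endpoint is not the number behind the power.

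**2. How many slots could be affected.** The documents give no dropout rate. If 5%, 10% or 20% of the 40 evaluable places were filled by replacement (assumed), that is 40 × 0.05 = 2, 40 × 0.10 = 4 or 40 × 0.20 = 8 places. At 10% or 20%, 1 or 2 of the 10 BAC places would be filled outside the schedule. The 30 v 10 contrast has only about 40% power (t-test) for 39.6 mg/L, so it has little room for non-random slots.

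**3. Can the replaced participant drop out of the analysis?** Setting the SAP sections side by side:

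- 6.1 sets one explicit data condition: at least one post-baseline CRP. *Evaluable* is left open.
- 6.2 removes early study withdrawals and early drug discontinuations when defining the per protocol set. That step would be largely redundant if they were already outside the primary set.
- 9.1 puts all available data into the models.

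The likeliest reading is that a replaced participant with a post-baseline CRP stays in. The clear way out is to have none, for example through death before dosing, which Protocol 8.8 lists. Exclusion of others depends on how someone later reads *evaluable*.

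**4. Size if replaced participants were wholly excluded.** Assumptions, none taken from the documents: *k* dornase alfa patients are replaced and all their data are dropped; their CRP lies 1 SD above the rest; there is no true effect and no covariate adjustment.

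- Fall in the active mean = k/(30 + k) × 62 mg/L.
- Shift of the test statistic = k/(30 + k) × √(30 × 70/100), for 30 active v 70 controls (60 historical + 10 BAC).
- Actual two-sided level = 1 − Φ(1.96 − shift) + Φ(−1.96 − shift).

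| k | k/(30 + k) | Fall in mean | Share of 39.6 | Shift | Level, 30 v 70 | Level, 30 v 60 |
|---|---|---|---|---|---|---|
| 2 | 0.0625 | 3.9 mg/L | 10% | 0.29 | 5.9% | 5.9% |
| 3 | 0.091 | 5.6 mg/L | 14% | 0.42 | 7.0% | 6.9% |
| 5 | 0.143 | 8.9 mg/L | 22% | 0.65 | 10.0% | 9.8% |

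The 30 v 60 column uses √(30 × 60/90). With a gap of 0.5 SD, the 30 v 70 levels are 5.2%, 5.5% and 6.2%. If the same patients stay in, the arm simply has 30 + k members and this bias is zero.

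**The case against.** **The SAP already protects the primary set.** Sections 6.1, 6.2 and 9.1 together point to keeping withdrawn participants who have any post-baseline CRP. A reader might infer that replacement contradicts the ITT statement. It would do so only if the replaced participant were also excluded, and no section says that. This part of the objection stands.

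**Progressing patients would usually be retained.** A reader might infer that patients whose disease progresses are swapped out of the dornase alfa arm. Protocol 8.8 lists progression as a reason for stopping treatment, not follow-up. Such a patient has normally been dosed, and CRP is scheduled on Days 1, 3, 5 and 7 and measured routinely, daily or on alternate days. Most would therefore meet SAP 6.1. This stands too, except that Protocol 8.9 does not separate withdrawal from treatment from withdrawal from the study.

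**It is not confined to one arm.** Protocol 8.9 covers both randomised arms, so the idea that poor responders leave the active arm only is not supported. Historical controls cannot withdraw, but BAC patients can.

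**Most of the primary comparison is not randomised anyway.** All controls in the Protocol's primary population are historical, as are 60 of 70 in the SAP's. Lost concealment in a few slots therefore matters mainly where randomised BAC patients are used.

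**Prediction before consent is an inference.** Protocol 8.2 places central randomisation after consent and eligibility, and 8.9 says *may* without stating who designates a replacement or when. That limits how far one can claim staff know the arm in advance. It does not restore random allocation: the arm still follows from who left.

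**Conclusion.** The allocation problem follows directly from the text. A same-arm replacement is outside the randomisation schedule and its arm can be predicted in an open-label trial. Its reach is limited: chiefly SAP 8.3.1 analysis 1, and the 10 BAC patients within the SAP primary comparator.

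The analysis problem is an ambiguity, not a demonstrated exclusion. Because *evaluable* is undefined, a replaced participant could be left out of the primary analysis, but the SAP sections taken together suggest that most would not be. The figures of 3.9 to 8.9 mg/L, and 5.9% to 10.0% in place of 5%, are a conditional worst case. They require complete exclusion, an assumed 1 SD gap and an unadjusted comparison of single values, whereas the planned model uses repeated measures adjusted for baseline CRP. They show why the wording should be closed off; they do not estimate bias in this trial.

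**What to change.** 1. **Protocol 8.9:** replace the same-arm rule with a statement that any additional participant takes the next concealed number on the randomisation schedule. Align Protocol 11.2.1 and SAP section 5 with it, and reconcile *may* with *will*.
2. **Protocol 11.3.1 and SAP 6.1:** state that every randomised participant with at least one post-baseline CRP stays in the primary analysis, in the assigned arm, with all CRP collected (including after stopping treatment), whether or not replaced. Report by arm those with no post-baseline CRP. This gives *evaluable* a fixed meaning.

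The cost is wording in both documents. Extra recruitment remains possible. The one drawback is that the final split may differ slightly from 30:10, because on average only three in four added participants go to dornase alfa, whichever arm the leaver was in.
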